Potential participants will be ages 7 to 17 years old; have a diagnosis of CAD (i.e., generalized anxiety disorder, separation anxiety disorder, specific phobia, panic disorder with or without agoraphobia) or OCD; and have at least one fear fitting exposures covered by the VR system. Qualifying diagnoses will be based on standardized assessments in the Clinic (MiniKIDS). Potential participants will be excluded if they have a high likelihood of being lost to follow-up or contact; are unable to provide good data; have significant comorbidity that would interfere with participation (e.g., uncontrolled oppositional defiant disorder) or are at heightened risk of self-harm (e.g., presence of active suicidal ideation reported on clinical interview or endorsement on a self-report measures, such as the PHQ-9M). Research assistants (RA) will approach eligible patients and describe the study. The RA will then obtain written informed consent from the parents and written informed assent from the child. Every effort will be made to enroll subjects in proportion to the gender and racial/ethnic demographics of the treatment population.

Study Protocol

Following recruitment and consent and assent, participants will be randomly assigned to the intervention or control condition. Then, participants will complete a baseline study session with study staff at the Clinic. At this session, the staff member will follow a standardized protocol to instruct all participants and their parents on how to use the exposure tracking form to electronically record exposure practice. Because all study participants will have started treatment in the Clinic, including orientation to parent-coached exposure, participating families

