
Participants will then be assigned one week of daily exposure homework with or without VR, depending on condition, using a paper exposure tracking form to record each exposure and SUDS. Patients randomized to intervention will take home the VR system for homework completion, and participants assigned to control will not take the VR system home and will be instructed to complete imaginal exposures. Participants will be asked to record each exposure, even if it is not related to the fear addressed with the baseline exposures, in order to capture all exposures completed during the homework period.

One week after the baseline session, all participants will return for a follow up session in which they complete both types of exposure (order randomized) and will receive an assignment to complete in their next Clinic therapy appointment a third generalization exposure, i.e., an exposure related to the baseline exposure that is higher on the fear ladder for the targeted fear, following procedures analogous to the baseline session. During the follow up session, staff from Clinic Health Care Policy & Research ("the interviewer") experienced in qualitative data analysis and not involved with the patients' medical care or development of the prototype system will observe, record, and code participants' engagement in the exposures and will interview participants about their experience with both types of exposure and then will ask for observations and opinions from the parent. A psychologist from the Clinic Health Care Policy & Research will work with the two lead child psychologists to identify questions and topics for a

semi-structured interview guide. The guide will be pilot-tested to ensure that questions and follow-up probes are easily comprehended and delivered in a sensitive manner. The semi-structured guide will follow guidelines for minimizing bias and increasing the reliability and validity of interview data[64,65]. All interviews will be audio-recorded.

During the participants' next therapy session, they will complete the assigned generalization exposure. SUDS ratings will be recorded for that exposure using the paper exposure tracking form, and participants will wear a sensor to obtain biometrics during the exposure.

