The primary outcomes of the study are: (1) difference in maximum SUDS ratings during time 1 exposures between VR and conventional, 2) difference in number of exposures completed to assigned item (as well as overall) between conditions; 3) difference in maximum SUDS rating in cross over exposure between conditions during time 2; and 4) difference in maximum SUDS rating in generalization exposure between conditions during time 2. We will also conduct exploratory analyses to see if decrease in anxiety symptoms, as measured by the Spence Child Anxiety Scales, Child and Parent reports, and improvement in functional impairment, as measured by the Child Sheehan Disability Scale, differ between groups.

Quantitative analysis: Descriptive and inferential statistics will be used, including means, standard deviations, medians, ranges, frequency distributions, t-tests, and Analyses of Variance (ANOVAs). Specifically: a) differences in maximum SUDS ratings during VR and traditional exposures during time 1 session will be examined using a paired-samples t-tests, b) change over time in the peak anxiety ratings for each modality (VR vs. imaginal) will be examined using Repeated Measures ANOVAs with VR status as the between subjects variable and change in anxiety rating (T1 to T2 difference in maximal SUDS for VR vs. T1 to T2 difference in maximal SUDS for imaginal) being the within subjects variable, c) differences between homework exposure conditions, on maximal anxiety in the generalization exposure at time 2 controlling for time 1 maximal SUDS averaged across exposure conditions will be examined using Analyses of Covariance (ANCOVA) with homework condition as the between subjects variable and number of completed exposures and average maximum anxiety across the two time 1 exposures as the covariates; and d) ANCOVA will be used to compare average number of homework exposures completed to target item (as well as overall exposures) during the study time frame between the conditions (i.e. VR vs. imaginal) controlling for patient characteristics (age, sex, diagnoses). Exploratory analyses will compare change in anxiety symptoms from time 1 to time 2 between conditions, controlling for patient characteristics, and examining number of completed exposures as a mediator of change.

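### The only analysis of primary outcome 4 (generalization SUDS) adjusts for the number of completed exposures, which accrues after randomisation and is itself primary outcome 2

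*Combined protocol and SAP*

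**What the plan says.** The Analysis Plan section of the SAP lists four primary outcomes. The fourth is the "difference in maximum SUDS rating in generalization exposure between conditions during time 2". The second is the "difference in number of exposures completed to assigned item (as well as overall) between conditions". Neither is defined as an effect at a fixed amount of practice.

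Under Quantitative analysis, four specific analyses follow. Item a concerns time 1 SUDS, item b the change from time 1 to time 2 by modality, and item d the exposure count. Only item c deals with the generalization exposure. It is an ANCOVA with homework condition as the factor and "number of completed exposures and average maximum anxiety across the two time 1 exposures as the covariates". The opening clause of item c mentions control for time 1 SUDS only; the count appears for the first time in the covariate list, with no reason given.

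The plan treats the same kind of count as a result of condition elsewhere. In item d, "ANCOVA will be used to compare average number of homework exposures completed to target item" between conditions. The exploratory analysis of anxiety symptoms proposes "examining number of completed exposures as a mediator of change", although for symptom change and not for generalization SUDS.

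The Study Protocol section fixes the order of events: "Following recruitment and consent and assent, participants will be randomly assigned to the intervention or control condition"; after the baseline session, "Participants will then be assigned one week of daily exposure homework with or without VR, depending on condition"; and the generalization exposure is done at the therapy session after the follow-up visit.

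**The concern.** Randomisation protects a comparison only when the model adjusts for things that condition cannot have changed. Time 1 SUDS is suitable in principle. The exposure count is not, because it lies between randomisation and the generalization exposure, and whether condition changes it is one of the trial's own primary questions.

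Adjusting for it can go wrong in two ways. If more practice lowers SUDS, the adjustment takes out the part of the effect that works through practice. If an unmeasured trait such as motivation drives both practice and SUDS, comparing arms at equal counts compares children who differ in that trait, and an effect can appear where none exists. Both require that condition changes the count. The two primary analyses therefore conflict in exactly the case that outcome 2 is meant to detect, and no specified analysis of outcome 4 omits the count.

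**Working it through.** **Inputs.** From the documents: the order of events, the covariates of item c, and the definitions of outcomes 2 and 4. The documents state no sample size, SD, alpha or effect size, so there is no figure of the plan's to reproduce. The rest is assumed:

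- 30 per arm (also 15 and 50); two-sided alpha 0.05
- residual SD 1.5 for the count and, separately, 1.5 for SUDS
- time 1 SUDS with SD 1.5 and slope 0.5
- d = extra exposures under VR: 0.5, 1 or 2
- s = SUDS reduction per exposure: 0.3 or 0.5
- m = SUDS reduction per SD of unmeasured motivation: 0.4 or 0.8; motivation raises the count by 1.0 per SD

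Each setting was simulated 20,000 times, fitting SUDS on condition and time 1 SUDS, with and without the count.

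**A. No true effect, shared motivation (s = 0).** Within an arm the count has variance 1.0² + 1.5² = 3.25, and the slope of SUDS on the count is -m/3.25. The adjusted condition coefficient is 0 - d × (-m/3.25), so bias = d × m / 3.25. For example, 0.5 × 0.4 / 3.25 = 0.06 and 2 × 0.8 / 3.25 = 0.49.

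| Extra exposures d | Bias / type I error, m = 0.4 | Bias / type I error, m = 0.8 |
|---|---|---|
| 0.5 | 0.06 / 5.1% | 0.12 / 5.9% |
| 1 | 0.12 / 6.1% | 0.25 / 8.2% |
| 2 | 0.25 / 8.0% | 0.49 / 16.3% |

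Over the same grid, type I error is 5.0% to 10.0% at 15 per arm and 5.3% to 24.5% at 50 per arm. With d = 0 there is no bias. If VR lowers the count, the bias changes sign. The model without the count stays near 5% throughout.

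**B. Effect wholly through practice, no shared cause.** True effect = -d × s, from -0.5 × 0.3 = -0.15 to -2 × 0.5 = -1.0. The model without the count recovers it, with 7% to 61% power. The planned model estimates about 0.00 and rejects about 5% of the time.

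**C. Direct effect of -0.5 plus practice, no shared cause.** Total = -(0.5 + d × s). The planned model returns -0.5, so the fraction removed is d × s / (0.5 + d × s).

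| d | s | Total effect | Planned model | Removed |
|---|---|---|---|---|
| 1 | 0.3 | -0.80 | -0.50 | 0.3/0.8 = 38% |
| 1 | 0.5 | -1.00 | -0.50 | 0.5/1.0 = 50% |
| 2 | 0.3 | -1.10 | -0.50 | 0.6/1.1 = 55% |
| 2 | 0.5 | -1.50 | -0.50 | 1.0/1.5 = 67% |

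Power falls from 48%-92% without the count to 18%-22% with it.

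**Both mechanisms together.** A separate large-sample check (400,000 participants per setting, motivation effect on SUDS set to 1.0) with d = 2, s = 0.5 and direct effect -0.5 gave -1.50 without the count and +0.11 with it (theory: -0.5 + 2/3.25 = +0.12). The two models agreed whenever condition did not change the count, and also when the count neither affected SUDS nor shared a cause with it.

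**The case against.** The strongest reply is that items c and d may be an intended pair: d asks whether VR changes the amount of practice, and c asks whether VR helps at equal practice. That is a coherent question. But outcome 4 is not worded that way, and the opening clause of item c names only time 1 SUDS. A direct-effect reading also needs the assumption that no unmeasured factor drives both count and SUDS, which the plan does not state.

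Second, every magnitude rests on assumed inputs, and the harm is conditional. This stands. In scenario A at 30 per arm, five of the six settings give type I error of 5.1% to 8.2%; the 16.3% needs a shift of 2 exposures, or 2/√3.25 = 1.1 within-arm SDs, with the stronger motivation effect. The loss of a practice-mediated effect in B and C, however, needs no unmeasured factor at all.

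Third, the direction deserves care. In scenario A, a higher count under VR gives a positive bias, so VR looks worse; in B and C a benefit of VR is understated. A spurious benefit would need another pattern, such as VR lowering the count.

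Two smaller points also stand. Item c does not say whether its count is for the assigned item or overall, so its identity with outcome 2 is inferred, though outcome 2 covers both. And the general list of descriptive statistics would allow raw arm means to be shown, which is a partial safeguard; no inferential analysis without the count is assigned to outcome 4.

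**Conclusion.** The concern holds. As written, the sole specified analysis of primary outcome 4 conditions on a post-randomisation variable that the plan also tests as a primary outcome, so its coefficient need not be the difference that outcome 4 asks for. That follows from the text and requires no numerical assumption. Whether the result is materially distorted depends on condition changing the count and on the count being related to SUDS. The documents do not settle either point, nor the direction. Under the assumed inputs, the consequences range from none to loss of the whole effect (B), and to bias of up to about half a SUDS point under the null (A).

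**What to change.** Remove the exposure count from the covariates of item c, so that the main analysis of outcome 4 is: generalization maximum SUDS = homework condition + average time 1 maximum SUDS. This also brings the covariate list into line with item c's own opening clause.

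If a comparison at equal practice is wanted, keep the count-adjusted model as a secondary or exploratory direct-effect analysis. Label it as such, say which count is used, and state the assumption of no unmeasured common causes of count and SUDS. Item d continues to report the count by condition.

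The cost is one phrase in the SAP and, optionally, one sentence for the secondary analysis. No new data, extra patients or change to study procedures are needed.

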**Low-Cost, Virtual Reality System to Increase Access to Exposure Therapy for
Anxiety and Obsessive Compulsive Disorders**

NCT 03636022

Date: 5/15/2024

Study Protocol

Children with childhood anxiety disorders (CADs) or obsessive compulsive disorder (OCD) and a parent will be recruited to test the VR system with a randomized controlled mixed methods study. Participants will be identified by through a Pediatric Anxiety Disorders Clinic using purposive sampling methods. All patients complete a standardized diagnostic assessment (including the MINI KIDS and Spence Child Anxiety Scales, Parent & Child report and begin treatment with psychoeducation on parent-coached exposure therapy for anxiety and OCD, create a treatment plan (i.e., fear hierarchy), and proceed to treatment sessions focused on completion of exposures. Participants will be recruited after their initial assessment and will begin the study in the early stages of treatment after completing psychoeducation and treatment planning.

Participants will be randomly assigned to home exposure practice with or without the VR system, i.e., intervention or control, respectively. All participants in the study will participate in an introductory session in which they complete two exposures related to content from their fear ladder, one with the VR system and an analogous imaginal exposure. Each family will receive instructions for how to use the exposure tracking form to record exposures during home practice. Participants will then be assigned one week of daily exposure homework for both the intervention and control conditions. Patients randomized to the intervention condition will take home the VR system for homework completion and participants assigned to control will be instructed to complete imaginal exposures. One week after the introductory session, all participants will return for a session in which they complete both types of exposure. They will also be assigned third generalization exposure, i.e., an exposure related to the baseline exposure that is higher on the fear ladder, to complete at their next anxiety clinic treatment session. Subjective Units of Distress (SUDS) ratings for each type of exposure will be recorded on paper with the exposure tracking form. During the follow up session, an independent interviewer will observe participants' engagement during exposures and will interview participants and their parents about their experience with both types of exposure.

Study Population

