Thus, study participation will include the two study sessions, completion and recording of exposures for one week between study sessions, and completion of a study-assigned exposure in a subsequent Clinic therapy session. Participation consent and assent will include agreement for clinically gathered assessments to be used for the study (i.e., initial structured interview, symptom rating scales completed at initial evaluation and clinic treatment follow up, number of treatment sessions attended, length of treatment). Study participants will continue with any treatment as usual during study participation.

Participant Recruitment & Participation Flow

Initial Clinic visit	Baseline Study Visit	1 week out-of-session exposure	Follow up Study Visit	Next Therapy Session	End of treatment assessments
Complete diagnostic interview & questionnaires as part of usual clinic procedures; If the patient meets study criteria, the Clinic psychologist/therapist will invite the patient and parent to participate	Informed Consent/Assent. 2 Baseline exposures. Participant will wear a sensor to obtain biometrics and SUDS ratings will be collected.	Participants will be instructed to practice daily either the VR exposure or imaginal exposure, depending on study condition, and to record exposures using the exposure tracking form	Repeat 2 baseline exposures. Participant will wear a sensor to obtain biometrics and SUDS ratings will be collected. Participants assigned generalization exposure to complete in next therapy session Qualitative interview and observation. Complete the Spence Child Anxiety Scales and the Child Sheehan Disability Scale. Participant will wear a sensor to obtain biometrics.	Participant will complete the assigned generalization exposure during therapy session following the Follow up Study Visit Participant will wear a sensor to obtain biometrics and SUDS ratings will be collected.	Participants complete questionnaires as part of usual clinic procedures. Study staff records data related to treatment length and # treatment sessions. Post-Treatment from Clinic
Participants continue with any treatments as usual, including treatment through Clinic					

Statistical Analysis Plan

Analysis Plan

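### The exploratory Spence comparison leaves out the initial Spence score, which costs precision; the mediation analysis states no assumption about confounding of exposure count, and baseline adjustment alone would not settle that

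*Combined protocol and SAP*

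**What the plan says.** The Analysis Plan names as exploratory outcomes "decrease in anxiety symptoms, as measured by the Spence Child Anxiety Scales, Child and Parent reports", together with functional impairment. The Quantitative analysis paragraph then plans: "Exploratory analyses will compare change in anxiety symptoms from time 1 to time 2 between conditions, controlling for patient characteristics", and adds "examining number of completed exposures as a mediator of change". No model is named and no initial symptom score is listed.

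The term patient characteristics is spelled out once, in item (d) just before: "controlling for patient characteristics (age, sex, diagnoses". Item (c), on the generalization exposure, does adjust for a starting value. It takes "number of completed exposures and average maximum anxiety across the two time 1 exposures as the covariates".

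An initial Spence score is available. The opening Study Protocol section states: "All patients complete a standardized diagnostic assessment (including the MINI KIDS and Spence Child Anxiety Scales, Parent & Child report". The consent paragraph before the participation flow table allows study use of "symptom rating scales completed at initial evaluation and clinic treatment follow up". In that table the Follow up Study Visit carries the instruction "Complete the Spence Child Anxiety Scales and the Child Sheehan Disability Scale". The Baseline Study Visit lists no Spence.

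**The concern.** There are two separate issues.

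**Precision of the randomised comparison.** A change score subtracts the whole initial score, including its measurement error. When the correlation between the two scores is below 1, regressing on the initial score leaves less residual variance. The plan gives up that gain although the covariate is already collected and precedes randomisation.

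**Interpretation of the mediated effect.** Condition is randomised, but the number of completed exposures is not. Its path to symptom change can be read causally only if the common causes of count and change are dealt with. Initial severity is an obvious candidate: it may influence how much a child practises, and a high first score tends to fall. The plan states no assumption on this and offers no second model. At stake is whether the trial reports, or misses, extra practice as the route by which VR homework changes symptoms.

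**Working it through.** The documents give no sample size, effect size, standard deviation or correlation, so there is no planned figure to reproduce. Every numerical input below is an assumption.

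**Inputs (assumed).** Spence scores have SD 1 at both times. rho is the within-arm correlation of initial and follow-up scores (0.6, 0.7, 0.8). r is the within-arm correlation of the measured initial score with exposure count (0.3). a is the effect of condition on count, in SD of count (0.5 or 0.8).

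**Step 1: precision.**
- Variance of change: 1 + 1 - 2rho = 2(1 - rho).
- Residual variance given the initial score: 1 - rho².
- Ratio: (1 - rho²) / [2(1 - rho)] = (1 + rho)/2.
- At rho 0.6, 0.7 and 0.8 the ratio is 0.80, 0.85 and 0.90. The change-score analysis would need 1/0.80 = 1.25, 1/0.85 = 1.18 or 1/0.90 = 1.11 times as many children for equal precision.

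In simulation the between-condition effect on change was unbiased in every scenario, as randomisation implies.

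**Step 2: mediation when count depends on the measured initial score.** Suppose exposures have no effect. Given arm, the covariance of change with count is rho·r - r = -r(1 - rho), and the variance of count is 1. The change-score model therefore gives a false slope of -r(1 - rho) and a false indirect effect of -a·r·(1 - rho). Adding the initial score gives zero.

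**Step 3: mediation when count depends on stable true severity.** Suppose the initial score is true severity plus error, with reliability rho. Count is then equally related to the initial and follow-up scores, so its covariance with change is zero and the change-score model is unbiased. The baseline-adjusted slope is (r - r·rho)/(1 - r²) = r(1 - rho)/(1 - r²), which is false.

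| rho | Step 2: change-score slope | Indirect effect, a = 0.5 / 0.8 | Step 3: adjusted slope | Indirect effect, a = 0.5 / 0.8 |
|---|---|---|---|---|
| 0.6 | -0.12 | -0.060 / -0.096 | 0.12/0.91 = +0.13 | +0.066 / +0.105 |
| 0.7 | -0.09 | -0.045 / -0.072 | 0.09/0.91 = +0.10 | +0.049 / +0.079 |
| 0.8 | -0.06 | -0.030 / -0.048 | 0.06/0.91 = +0.07 | +0.033 / +0.053 |

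All signs reverse for r = -0.3, and every indirect effect is zero if r or a is zero. Simulations with 1,000,000 children per scenario agreed: the step 2 indirect effects at a = 0.5 and the step 3 slopes were reproduced.

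**Step 4: a real effect can be hidden either way.** Take a = 0.5, rho = 0.7 and a true indirect effect of -0.05.
- If count depends on the measured score (correlation -0.3), the change-score model gives -0.005 and the adjusted model -0.050.
- If count depends on true severity (correlation with true severity +0.3), the change-score model gives -0.050 and the adjusted model -0.009.

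**Step 5: what time 1 means.** The only earlier scheduled Spence is at the initial clinic assessment, before psychoeducation and treatment planning. Change measured from that score includes early clinic treatment as well as the study week. A longer interval may also lower rho, which would increase the gain in step 1.

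**The case against.** The strongest case against has four parts.

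- **The covariate list is inferred.** The plan names no model for this analysis, and the age, sex and diagnoses list belongs to item (d). This is fair. But the same term recurs in the next sentence with no new definition, and no initial Spence score appears anywhere in the analysis text.
- **Baseline adjustment is not a cure for the mediation path.** A reader might infer that adding the initial score removes the bias. It does so only if count depends on the measured score. Homework practice may plausibly follow true severity instead, and then the change-score model is right and adjustment does the harm (step 3). The documents cannot decide between the two. This objection stands in full.
- **Exposure count appears elsewhere.** A reader might infer that this is the only place where the plan relates count to an anxiety outcome. Item (c) also includes count as a covariate, with adjustment for time 1 SUDS, in the model for the generalization exposure. It is not a mediation analysis, but it does relate the two.
- **The sizes are assumed and small.** True: r, rho and a are not in the documents, and the false indirect effects are roughly 0.03 to 0.11 Spence SD. Against that, step 4 shows that a bias of this size can almost cancel a real indirect effect of 0.05 SD.

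**Conclusion.** The point holds in two parts, both of low priority because the analysis is exploratory.

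1. **The randomised comparison loses precision that is free to recover.** The variance ratio of 0.80 to 0.90 rests on equal variances at the two times and an assumed rho of 0.6 to 0.8. A reader might infer from the missing covariate that the comparison between conditions is biased. It is not, because condition is randomised.
2. **The mediated effect is open to confounding in either direction.** It needs both an effect of condition on count and a link between severity and count. The documents quantify neither, so the bias is possible, not demonstrated. Neither the change-score model nor the baseline-adjusted model is safe without an assumption that the plan does not state.

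**What to change.** **Between-condition comparison.** Specify an ANCOVA with the same reporter's initial-evaluation Spence score as a covariate, besides age, sex and diagnoses, run separately for child and parent report. With that covariate in the model, follow-up score and change score give the same condition effect, so either may be the outcome. State that Spence time 1 is the initial clinic evaluation score.

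**Mediation.** Report the baseline-adjusted model and the change-score model side by side as a sensitivity analysis. State the no-confounding assumption for exposure count and symptoms, and label the indirect effect observational. If the two models disagree, report that the data do not settle the mediated effect.

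**Cost.** SAP wording, one degree of freedom per model that gains the covariate, and one additional mediation model per reporter. No new data collection is needed.
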